### 9.1 Description of Correlative studies:

#### 9.1.1 The role of EpHB4 in driving mCRPC

Abundant evidence from human and transgenic mouse studies indicate that alterations in key cancer genes, including MYC, an oncogene and PTEN, a tumor suppressor and negative regulator of PI3K activity can conspire to lead to aggressive prostate cancer [23]. EphB4 supports cMYC expression at transcriptional level in

colon cancer [25]. Further, kinomic analyses of EphB4 mutations in lung cancer revealed the involvement of PTEN or TP53 loss, and activation of EGFR or IGF1R pathways [26]. EphB4 can promote tumorigenesis by engaging multiple signaling pathways, including the PI3 kinase/AKT pathway [27]. We are particularly interested in determining if sEphB4-HSA treatment modulates PI3K/AKT pathways in Myc driven tumorigenesis. For this, we will evaluate the expression of MYC, PI3K and downstream mediators pS6K.

In addition to PI3K pathways, preliminary studies from [name] and [name] laboratories show that the expression of EphB4 level is retained after Androgen Deprivation Therapy (ADT), indicating that it can be a target in cancers after ADT. We also want to explore if sEphB4-HSA cooperates with enzalutamide or abiraterone. There is an interesting relationship between the PI3K and AR pathways in castration-resistant prostate cancer with therapeutic implications. Combining AR inhibition with PI3K inhibition may be an effective strategy for treating Pten-null CRPC [28]. As shown in the preliminary results, sEphB4 treatment inhibits that PI3K pathway, thereby providing a rationale for combining sEphB4 with AR pathway inhibition. We will evaluate the expression of AR in primary and metastatic tissue of patient and correlate the status of AR as a predictive biomarker for response to sEphB4-HSA treatment.

Mechanistically, sEphB4-HSA acts by binding to Ephrin B2 and preventing its binding to EphB4. Given the cooperation between Ephrin B2 expressing endothelial cells and EphB4 expressing tumor cells [29], it is important to investigate the expression of both molecules in this treatment setting. To this end, we will evaluate the expression of EphB4 and Ephrin B2 in the tumor microenvironment of patient tissue and correlate to treatment response.

We also aim to understand the impact of sEphB4-HSA treatment on the tumor microenvironment in general and immune cell infiltration to the metastatic tumor site in particular. Ephrin B2, the binding partner of sEphB4-HSA and EphB4 receptor plays a prominent role in suppression of activated T cells [30]. Our preliminary *in vivo* studies showed the increase of CD3 cells in transgenic mice (Pten-,Myc+ P53-) treated with sEphB4-MSA. Therefore, it is worthwhile to study tumor-infiltrating lymphocytes in tumor tissues from baseline evaluation and response evaluation time points. Specifically, we will investigate the expression of CD4+ Helper T cells and CD8+ Cytotoxic T cells, and CD31+ Endothelial cells.

#### **9.1.2 EphB4 activation and other associated genes as a biomarker for response**

EphB4 is known to be upregulated in most cancer tissues. Furthermore, preclinical evidence from mouse model of aggressive prostate cancer with Myc amplification and PTEN showed significant tumor regression following EphB4 targeted therapy. Therefore it is of high significance to identify genomic alterations in EphB4 and other associated genes like Myc, p53, PI3k and AR to predict clinical response. We will analyze standard of care genetic/genomic/NGS testing reports to identify genetic alterations including MYC, AR, P53 and other most commonly mutated cancer driver genes. We will also analyze through immunohistochemistry the baseline level of EphB4 and Ephrin B2 and the molecular drivers of mCRPC mentioned in 9.1.1, their co activation with EphB4 and contribution to development of mCRPC [18].

#### **9.1.3 The landscape of genomic alterations in the course of sEphB4 treatment**

CfDNA has emerged as an efficient non-invasive biomarker that not only correlates to cancer stage and response to therapy but also identifies somatic mutations acquired with therapy predicting pathways involved in drug resistance [31]. cfDNA will be

isolated from the blood samples and stored for future analysis and analyzed by NGS testing

#### **9.2 Sample Collection Guidelines**

From each patient, specimens will be collected as below:

- a. If available, archival tissue of primary tumor and metastatic tumor will be obtained.
- b. Blood for cfDNA (pre-treatment, Cycle 3 Day 1 and at clinical progression or when off study, whichever is first)

Please refer to Lab Manual for instructions on sample collection.

#### **9.3 Sample Processing, Storage, and Shipment**

See the Lab Manual for instructions on sample processing, storage and shipment.

#### **9.4 Assay Methodology**

##### **9.4.1 Immunohistochemistry:**

For metastatic and primary tumor samples we will follow the standard protocol for immunohistochemistry to perform qualitative and quantitative measurement of EphB4, EphrinB2, PI3K-AKT pathway, MYC, PTEN pathway, AR, and for markers of Tumor Infiltrating lymphocytes and endothelial cells For immune cell staining, the pathologist will assign scores of 0, 1+, 2+ or 3+ based on staining intensity and percent positive cells per unit area of section

##### **9.4.2 Next Generation Sequencing**

cfDNA samples will be analyzed by NGS assays at Northwestern University.

#### **9.5 Specimen Banking**

Research samples will be stored at the [name] Lab or Northwestern University Pathology Core Facility until the material has been exhausted or the repository is discontinued after the trial is completed. If the repository is permanently closed, all stored sample material will be destroyed. Samples may be maintained beyond the death of the participant.

### **10 STATISTICAL CONSIDERATIONS**

This is a single-arm study evaluating the efficacy, safety, and tolerability of sEphB4-HSA in patients with mCRPC. Analysis populations are defined below.

#### **10.1 Sample size and Statistical and data analysis plan for the primary objective.**

To estimate **preliminary efficacy** we will assess PSA response rate (PR and CR) with a **Simon two stage minimax design**. We assume the undesirable overall response rate (null hypothesis) to be approximately 10% or less, and the alternate hypothesis suggesting success to be approximately 30% or more. Fifteen patients will be added in the first stage. If 2 or more respond, then an additional 10 patients will be added for a total of 25 evaluable patients. If not, we will stop the study after the first stage. The study will be assessed by the DSMC for excess toxicity at this point in time and stopped if DSMC finds excessive toxicity. If the second stage is completed, five or fewer successes will suggest failure and six or more responses a success of the entire study. This design has a Type I error rate of less than 5% and 80% or greater power. It has a 55% chance of stopping early after the first stage if the true response rate is 10% or less, and a total expected long run average sample size of n=19.5. See below, using Pass 11 software.

**Two-Stage Clinical Trials Sample Size**  
**Possible Designs For P0=0.100, P1=0.300, Alpha=0.050, Beta=0.200**

N1	R1	PET	N	R	Ave N	Alpha	Beta	Constraints	
								Satisfied	
25	5	0.000	25	5	25.00	0.033	0.193	Single Stage	
15	1	0.549	25	5	19.51	0.033	0.198	Minimax	
10	1	0.736	29	5	15.01	0.047	0.195	Optimum	

**Report Definitions**

N1 is the sample size in the first stage.

R1 is the drug rejection number in the first stage.

PET is the probability of early termination of the study.

N is the combined sample size of both stages.

R is the combined drug rejection number after both stages.

Ave N is the average sample size if this design is repeated many times.

Alpha is the probability of rejecting that  $P \leq P_0$  when this is true.

Beta is the probability of rejecting that  $P \geq P_1$  when this is true.

P0 is the response proportion of a poor drug.

P1 is the response proportion of a good drug.

PSA response rate will be reported with two-sided 80% exact binomial confidence interval (corresponding to the one-sided  $\alpha=0.10$ ).

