## **2 OBJECTIVES**

### **2.1 Primary Objective:**

- 2.1.1 To estimate the efficacy of sEphB4-HSA in patients with mCRPC as measured by confirmed PSA response rate.

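### The planned 80% interval for the PSA response rate takes no account of the stop after 15 patients, so its upper limit is somewhat too low for 2 to 4 responses in 25

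*Combined protocol and SAP*

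**What the plan says.** The primary objective (section 2.1) is "To estimate the efficacy of sEphB4-HSA in patients with mCRPC as measured by confirmed PSA response rate". In section 10.1 the plan says that "we will assess PSA response rate (PR and CR) with a Simon two stage minimax design". The null rate is stated in these words: "We assume the undesirable overall response rate (null hypothesis) to be approximately 10% or less". For the target, section 10.1 takes a rate of about 30% or higher.

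On the stages, section 10.1 says: "Fifteen patients will be added in the first stage". It goes on: "If 2 or more respond, then an additional 10 patients will be added for a total of 25 evaluable patients". With fewer than 2 responders: "If not, we will stop the study after the first stage". At 25 patients, 6 or more responses count as success and 5 or fewer as failure.

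The reporting statement comes at the end of section 10.1, under Report Definitions: "PSA response rate will be reported with two-sided 80% exact binomial confidence interval". The plan ties this interval to a one-sided alpha of 0.10, that is, 10% in each tail. Neither section 10 nor the Study Summary names an estimate or interval that allows for the stage 1 stop.

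**The concern.** An ordinary exact binomial interval assumes that the sample size was fixed in advance. Here it was not: a trial with 0 or 1 responders among the first 15 never reaches 25. Some of those trials would have ended with 4 or more responses had they continued. A low result at 25 therefore sits above a block of stopped trials that the fixed-sample formula does not count, and its upper limit comes out too low.

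The estimate and its interval are what remains of the primary objective when the trial misses 6 of 25. An upper limit that is too low overstates the evidence against the 30% target. The raw proportion also averages slightly below the truth, because stopped trials keep their low stage 1 rate.

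**Working it through.** **Inputs (section 10.1).** Stage 1 has n1 = 15 patients and continues if X1 ≥ 2. The total is N = 25, with success at S ≥ 6. The design rates are p0 = 0.10 and p1 = 0.30. The interval is 80%, so 10% per tail.

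**Step 1: reproduce the plan's design figures.** With X1 ~ Bin(15, p) and X2 ~ Bin(10, p):
- Early stop at 10%: P(X1 ≤ 1) = 0.549.
- Average size: 15 + 10 × (1 − 0.549) = 19.51.
- Alpha: Σ over x ≥ 2 of P(X1 = x) × P(X2 ≥ 6 − x) at 0.10 = 0.0328.
- Power, same sum at 0.30: 0.8017, so beta = 0.198.

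All agree with the minimax row of the table (0.549, 19.51, 0.033, 0.198).

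**Step 2: the two intervals.** The planned upper limit for s responses in N solves P(Bin(N, p) ≤ s) = 0.10. For the two-stage interval, the probability of reaching 25 with s responses is

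P(continue, S = s) = Σ over x ≥ 2 of C(15, x) × C(10, s − x) × p^s × (1 − p)^(25 − s).

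Stopped outcomes rank below all 25-patient outcomes. The two-stage upper limit solves P(stop) + Σ from j = 2 to s of P(continue, S = j) = 0.10. The lower limit solves P(continue, S ≥ s) = 0.10.

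| Result | Raw rate % | Planned 80% interval % | Two-stage 80% interval % | UMVUE % |
|---|---|---|---|---|
| 0/15 | 0.0 | 0–14.23 | 0–14.23 | 0.0 |
| 1/15 | 6.7 | 0.70–23.56 | 0.70–23.56 | 6.7 |
| 2/25 | 8.0 | 2.15–19.91 | 3.60–24.27 | 13.3 |
| 3/25 | 12.0 | 4.49–24.80 | 5.23–26.58 | 15.3 |
| 4/25 | 16.0 | 7.17–29.47 | 7.52–30.10 | 17.9 |
| 5/25 | 20.0 | 10.06–33.97 | 10.21–34.17 | 20.9 |
| 6/25 | 24.0 | 13.12–38.33 | 13.18–38.38 | 24.4 |

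The planned upper limits are out of order: 2/25, which passed stage 1, has a lower limit of plausibility at the top (19.91%) than 1/15, which failed it (23.56%). The two-stage limits rise steadily.

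**Step 3: upper-tail error of the planned interval.** Take a true rate just above 24.80%, the planned upper limit for 3/25. The outcomes whose upper limit lies below the truth are a stop at 15 (8.27%), 2/25 (0.92%) and 3/25 (4.34%). The sum is 8.27 + 0.92 + 4.34 = 13.53%, against a nominal maximum of 10%. The lower-tail error at that rate is 6.8%, so two-sided coverage is 79.7%, its minimum. At a true 30% the upper-tail error is 3.53 + 0.26 + 1.59 + 4.81 = 10.19%. The two-stage interval keeps both tails at or below 10%.

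**Step 4: bias of the raw rate.** The mean raw rate is 8.72% at a true 10%, 13.71% at 15%, 19.01% at 20% and 29.66% at 30%. The bias is therefore −1.28, −1.29, −0.99 and −0.34 points. It is largest, −1.35 points, near a true 12.5%.

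The UMVUE (uniformly minimum-variance unbiased estimate) for a 25-patient result is Σ C(14, x − 1) × C(10, s − x) divided by Σ C(15, x) × C(10, s − x), both over x ≥ 2. For 2/25 this is 14/105 = 13.3%. Its root mean squared error, against that of the raw rate, is 7.3 against 6.6 points at a true 10%, 8.2 for both at 15%, 8.8 against 9.2 at 20%, and 9.4 against 9.8 at 30%.

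**The case against.** A reader might infer that near misses in general would wrongly rule out the 30% target. The documents do not support that. The nearest miss under the plan's own rule is 5/25, and its interval includes 30% by either method. At 3/25, 2/25, 1/15 and 0/15 both methods exclude 30%. Only 4/25 changes, by about 0.6 point, and that result has probability 4.8% if the true rate is 30%.

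A reader might also infer that the trial's conclusion is at risk. It is not: success rests on the response count, and no section uses the interval as a criterion. Two-sided coverage never falls below 79.7%, so by that measure the planned interval is close to its stated level. What remains is the split between tails, where the upper one runs over.

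The bias argument has limits too. It is small on average, and among trials that reach 25 patients the raw mean is too high (14.3% at a true 10%, 30.5% at a true 30%). There the UMVUE lies further from the truth (17.1% and 30.9%). At 2/25 it equals 2/15, as if the 10 stage 2 non-responders had not been seen, and it would put a failed result above the 10% null when 8% was observed. This is a good case against making it the headline estimate, and it stands.

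Finally, the plan does not use the words single-stage. A fixed-sample interval is the ordinary meaning of exact binomial, and nothing in section 10 points elsewhere, but it remains a reading.

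**Conclusion.** The point holds as a minor reporting matter. The planned interval does not reflect the futility stop. Its upper limit misses the truth up to about 13.5% of the time instead of at most 10%, and the limits for 1/15 and 2/25 are out of order. The shift in the upper limit is 4.4 points at 2/25, 1.8 at 3/25, 0.6 at 4/25 and 0.2 at 5/25, and it is negligible or nil elsewhere. Results of 2 to 4 in 25 are not rare if the drug is weak: their combined probability is 9.3 + 14.8 + 11.6 = 35.8% (before rounding) at a true 10%, and 6.7% at a true 30%. Bias in the raw rate is at most about 1.35 points and 0.34 at the target. The 6-of-25 rule and its error rates are untouched.

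This rests on three assumptions: the planned interval is the fixed-sample (Clopper-Pearson) one on the number actually treated as evaluable; the stages close at exactly 15 and 25 evaluable patients; and patients respond independently at a common rate. The 80% level is taken as given; whether it suits the design's alpha is a separate question that this change would not settle.

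**What to change.** In section 10.1, replace the exact binomial interval for the PSA response rate with the exact two-stage interval that accounts for the stage 1 stopping rule, and state the ordering used (stopped outcomes below all 25-patient outcomes, then by number of responses). Keep the observed proportion as the reported rate and give the UMVUE beside it as a bias-adjusted estimate. Make the change before results are known, so that the choice of method cannot follow the data.

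The cost is a sentence or two in the plan and a short calculation. It needs no extra patients or data and leaves the decision rule alone. The downside is a somewhat higher upper limit for low results, and a second estimate that needs a line of explanation where it differs visibly from the observed rate, as at 2/25.

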**10.2 Analysis of secondary and exploratory objectives**

To estimate the distributions of time to PSA progression and rPFS (defined in Section 6.3), we will use Kaplan Meier methods, and estimate the median with two-sided 90% CI.

The estimated overall response rate in patients with measurable disease (Section 6.1.1) will be reported with two-sided 90% exact binomial CI.

For each patient within the population evaluable for toxicity (Section 6.1.1), recorded AE data over time will consolidated as the maximum grade observed of each AE type. All reported AE types will be tabulated by maximum grade using frequencies and percentages. Data on type, timing, frequency and attribution of AEs will also be summarized.

To explore if PSA response is associated with expression of EphB4 and ephrinB2 in archival metastatic and primary tumor CRPC specimens, and/or with aberrations in the PI3K pathway, P53, MYC. Marker values will be summarized according to PSA response status. Summaries will be descriptive and graphical; hypothesis testing is not planned.

**10.3 Accrual**

This multi-site trial will accrue patients at University of Chicago, University of Southern California and Northwestern University. Four-eight potentially eligible patients are seen per month at participating sites. Accordingly, we plan to enroll 1-2 patients per month. We expect it will take 18 months to accrue our study population.

**11 STUDY MANAGEMENT****11.1 Institutional Review Board (IRB) Approval and Consent**

It is expected that the IRB will have the proper representation and function in accordance with federally mandated regulations. The IRB should approve the consent form and protocol.

In obtaining and documenting informed consent, the investigator should comply with the applicable regulatory requirement(s), and should adhere to Good Clinical Practice (GCP) and to ethical principles that have their origin in the Declaration of Helsinki.

Before recruitment and enrollment onto this study, the patient will be given a full explanation of the study and will be given the opportunity to review the consent form. Each consent form must include all the relevant elements currently required by the FDA Regulations and local or state regulations. Once this essential information has been provided to the patient and the investigator is assured that the patient understands the implications of participating in the study, the patient will be asked to give consent to participate in the study by signing an IRB approved consent form.

Prior to a patient's participation in the trial, the written informed consent form should be signed and personally dated by the patient and by the person who conducted the informed consent discussion.

#### **11.2 Amendments**

The Principal Investigator will formally initiate all amendments to the protocol and/or informed consent. All amendments will be subject to the review and approval of the appropriate local, institutional, and governmental regulatory bodies, as well as by VasGene Therapeutics Inc. Amendments will be distributed by the lead institution (Northwestern) to all affiliate sites upon approval by the Northwestern University IRB.

#### **11.3 Registration Procedures**

For potential patients for this study, study teams are asked to inform the QAM of the date and time that the patient will need to be registered  
[\([contact]\)](mailto:[contact]).

BEFORE a patient can be treated on study, please complete and submit the following items to confirm eligibility and receive an identification number:

- Patient's signed and dated informed consent form (upload to NOTIS and keep original hard copy in a secure location/study chart)
- Eligibility checklist (signed and dated by the treating physician – upload to NOTIS)
- Eligibility eCRF (complete in NOTIS)
- Copy of the pathology report (upload to NOTIS)

The QAM will review all source documentation required to confirm eligibility that is readily available in the patient's electronic medical record (EMR). Any information that is not available in the EMR must be de-identified and emailed to the QAM. Once the QAM confirms the patient is eligible, he or she will register the patient, assign a subject identification number, provide a cohort assignment, and send a confirmation of registration to involved personnel. Registration will then be complete and the patient may begin study treatment.

#### **11.4 Data Submission**

Once a patient is confirmed and registered to the study, eCRFs should be submitted according to the study procedures table. Generally, for all phase II patients, data are due within 10 days of a visit. A set amount of data may also be requested for any screen failures, as is defined by the study. In most instances, this will include collection of adverse events and baseline data from the time of registration to the date of screen failure.

#### **11.5 Data Management and Monitoring/Auditing**

This study will be conducted in compliance with the Data Safety Monitoring Plan (DSMP) of the Robert H. Lurie Comprehensive Cancer Center of Northwestern University (please refer

to NOTIS for additional information). The level of risk attributed to this study requires *High Risk* as outlined in the [DSMP](#). The assigned QAM, with oversight from the Data Monitoring Committee, will monitor this study in accordance with the study phase and risk level. Please refer to the NOTIS for additional data submission instructions.

## **11.6 Adherence to the Protocol**

Except for an emergency situation in which proper care for the protection, safety, and well-being of the study patient requires alternative treatment, the study shall be conducted exactly as described in the approved protocol.

### **11.6.1 Emergency Modifications**

For any such emergency modification implemented, an IRB modification form must be completed within 5 business days of making the change, and the QAM must be notified within 24 hours of such change.

### **11.6.2 Other Protocol Deviations**

All other deviations from the protocol must be reported to the assigned QAM using the appropriate form.

A protocol deviation is any change, divergence, or departure from the study design or procedures of a research protocol that is under the investigator's control and that has not been approved by the Institutional Review Board (IRB). Protocol deviations must be reported according to the policies and procedures of the IRB of record.

A protocol deviation may be considered an instance of Promptly Reportable Non-Compliance (PRNC) if it:

- Has harmed or increased the risk of harm to one or more research participants.
- Has compromised the rights and welfare of the research subject
- Has damaged the scientific integrity of the data collected for the study.
- Results from willful or knowing misconduct on the part of the investigator(s).
- Demonstrates serious or continuing noncompliance with federal regulations, State laws, or University policies.

## **11.7 Investigator Obligations**

The Principal Investigator is responsible for the conduct of the clinical trial at the site in accordance with Title 21 of the Code of Federal Regulations and/or the Declaration of Helsinki. The PI is responsible for personally overseeing the treatment of all study patients. The PI must assure that all study site personnel, including sub-investigators and other study staff members, adhere to the study protocol and all FDA/GCP/NCI regulations and guidelines regarding clinical trials both during and after study completion.

The Principal Investigator at each institution or site will be responsible for assuring that all the required data will be collected, entered onto the appropriate eCRFs, and submitted within the study-specific timeframes. Periodically, monitoring visits may be conducted and the Principal Investigator will provide access to his/her original records to permit verification of proper entry of data. The study may also be subject to routine audits by the Audit Committee, as outlined in the DSMP.

